RESEARCH PROTOCOL

NCT03279458

Title	Non-invasive tidal volume monitoring using the Linshom Respiratory Monitoring Device
Faculty Sponsor	[name]
Principle Investigator/Co-investigators	[name] [name] [name]
Abstract	
Many post-operative complications arise from patients who breathe inadequately. Inadequate respiration, whether the result of surgery or the anesthesia, causes a decrease in blood oxygen saturation and an increase in carbon dioxide partial pressure. Both of these surrogate measurements of respiration may pose a challenge to measure. Some administer exogenous oxygen to all patients as they leave the operating room in order to maintain the blood oxygen saturation. This renders the oximeter a less sensitive metric of depressed respiration. In the face of decreased respiration, the carbon dioxide levels continue to increase slowly and often go undetected unless blood gases are measured. Indeed carbon dioxide blood levels are the only metric to detect inadequate ventilation using this surrogate index.
 
Monitoring ventilation is a serious challenge outside of critical care settings. In fact, there are no monitors available that can measure tidal volume or relative tidal volume outside of these settings.
 
Linshom is a novel instrument that tracks relative respiration by measuring the excursions of the temperature swings between inspiration and expiration and normalizing them to the patient's breathing. This monitor may be the first non-invasive monitor to measure relative tidal volume in non-critical care settings.


Background
	
Oxygenation – the process of delivering oxygen to the lungs – is often much simpler to achieve than ventilation, since only a small volume of oxygen must be delivered to oxygenate the patient and provide a reserve. Carbon dioxide, however, constantly accumulates and depends on ongoing ventilation to eliminate it from the lungs.
 
Direct automatic ventilation monitors tend to be cumbersome. They typically require chest straps or EKG-type stickers to be placed on the patient’s chest. EKG signals themselves can be used to detect inhalation and exhalation, but the noise of EKG monitors tends to make this method unreliable. In most cases, the patient needs to be lying quite still in order for accurate ventilation monitoring and even then they measure respiratory rate and not tidal volume.
 
The gold standard method to measure the adequacy of ventilation is to measure the exhaled carbon dioxide concentration. Exhaled gas almost always contains carbon dioxide that may be measured using either sidestream or mainstream capnography. However, the carbon dioxide tension is only a surrogate measure of ventilation since it is the changes in tidal volume per breath or minute ventilation that determines the adequacy of respiration and therefore the carbon dioxide tension. Capnography accurately measures the respiratory rate and the net effect of ventilation without reporting the tidal volume. Knowing the tidal volume before the carbon dioxide tension begins to increase provides an opportunity to intervene before the clinical situation has deteriorated too much. Linshom is a reliable, effective patient ventilation monitor that is minimally invasive, simple, inexpensive, fast responding and tracks relative tidal volume outside of critical care settings.

Purpose
	
To determine whether a non-invasive, temperature-based respiratory instrument could track tidal volume (V_t) in patients.

Specific Aim(s)
	
The primary purpose of this investigation is to evaluate whether a non-invasive, thermodynamic temperature-based instrument, Linshom, can accurately and consistently track tidal volume as measured by closed loop mechanical ventilator.

Study Period (inclusive years)
	
The study will be completed over a period of one week.


Study Design
	
Flyers advertising the study will be placed around campus on designated bulletin boards. Individuals interested in the study will be able to call the number (PI Office Number: [name]). If the individual meets the study criteria, then he or she will be scheduled for a study session, which will take place in room N200-13 of the respiratory therapy department. After completing the visit, the volunteer will receive a \$10.00 gift card.
 
The Linshom detector, which is comprised of two rapid responding medical-grade thermistors in close proximity to the mouth/nose (sensor) and a thermistor remote to the airway, will be mounted in the CPAP facemask to measure the temperature during breathing. The CPAP will be connected to a Servo-I ventilator (Maquet) with a circuit and disposable filter. The volunteers will be instructed to breathe normal through the CPAP mask on room air. The excursions of the thermistor tracings (from valley to peak) will be recorded by the Linshom device and displayed continuously on a laptop monitor in a waveform. The tidal volume will also be measured by the ventilator and the data downloaded in a Compact Flash card. The temperature profiles from the sensors and the relative tidal volume will be correlated with the tidal volumes measured by the ventilator.

Inclusion Criteria
	
Healthy volunteers 18 years of age or older will be recruited from the Medical School at the University of Mississippi.

Exclusion Criteria
	
Individuals who are pregnant, suffer from claustrophobia, or who have had a recent respiratory or gastrointestinal illness will be excluded. Volunteers deemed not to have the capacity to provide informed consent will not be enrolled.

Number of Subjects (anticipated)
	
40.

Outcome Measures
	
Every volunteer recruited in this study will be monitored by the study investigators during data collection. Linshom readings showing the temperature changes and tidal volume measured by ventilator will be collected.

Study Endpoints
	
The subjects will breathe through the mask for about 5 minutes, and will be observed during this time by the study investigators. Continuous data for tidal volume and temperature will be collected during this time and the data will be analyzed post-hoc.

Private Health Information	No medical record information will be collected – no other volunteer information will be recorded. Volunteer numbers will be paired with study numbers in a single Microsoft Excel spreadsheet. All study information will thereafter refer to study numbers.
Statistical Methodology	We shall correlate the tidal volumes measured with the Linshom detector with the respective tidal volumes from the mechanical ventilator. A least squares regression analysis (with the coefficient of determination r-squared) and a Bland Altman plot will be prepared. P<0.05 will be accepted.

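### The aim promises consistent tracking, but the plan names no unit of analysis and no per-volunteer measure, so no planned result can establish consistency

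*Combined protocol and SAP*

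**What the plan says.** Specific Aim(s) makes it the primary purpose to evaluate whether the device "can accurately and consistently track tidal volume as measured by closed loop mechanical ventilator". The protocol does not define consistency.

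Number of Subjects (anticipated) gives 40, without justification. Study Endpoints describes repeated data on each person: "The subjects will breathe through the mask for about 5 minutes", and "Continuous data for tidal volume and temperature will be collected during this time and the data will be analyzed post-hoc". Study Design limits the conditions: "The volunteers will be instructed to breathe normal through the CPAP mask on room air".

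The analysis, in Statistical Methodology, has three parts:

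- a correlation: "We shall correlate the tidal volumes measured with the Linshom detector with the respective tidal volumes from the mechanical ventilator";
- two outputs: "A least squares regression analysis (with the coefficient of determination r-squared) and a Bland Altman plot will be prepared";
- one criterion: "P<0.05 will be accepted".

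Study Design describes the comparison differently: "The temperature profiles from the sensors and the relative tidal volume will be correlated with the tidal volumes measured by the ventilator". One section therefore compares tidal volumes as such, and the other brings in relative tidal volume.

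No section says whether a data point is a breath, a volunteer's mean or a within-volunteer deviation. None names a correlation, slope, bias or limits for each volunteer, a between-volunteer variance component, or a count of volunteers in whom the device tracks. No threshold is set for r-squared or for the limits of agreement.

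**The concern.** A respiratory monitor is read on one person at a time, and according to the Abstract this one works relative to that person's own breathing. The natural meaning of consistent tracking is that it follows tidal volume within each wearer. The planned outputs need not show that. A regression over all breaths mixes two things: large breathers differing from small breathers, and each person's breaths varying from one to the next. Only the second is tracking, but the first can dominate r-squared.

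At stake is the wording of the conclusion. Following the plan as written, the trial could report a high r-squared with P<0.05 and conclude that tracking is consistent, although the device did not track at all in some volunteers.

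**Working it through.** **From the protocol.** 40 volunteers, about 5 minutes each, normal breathing, criterion P<0.05. There is no target r-squared, SD, agreement limit or power, so the plan has no figure to reproduce.

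**Assumed.**
- 12 breaths/min: 60 per volunteer, 2400 in all.
- Within-volunteer correlation ρ = 0.95 in trackers and 0 in non-trackers.
- Between-volunteer SD s_b = 100 to 150 mL; within-volunteer SD s_w = 50 to 100 mL, equal for both instruments.
- Every volunteer's Linshom readings, in mL, are centred on that person's true mean.
- f = share of volunteers who do not track.

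**1. Breaths pooled in mL.**
r² = [(s_b² + (1−f)ρs_w²)/(s_b² + s_w²)]². The extremes are s_b = s_w = 100 and s_b = 150, s_w = 50.

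| f | 100/100 | 150/50 |
|---|---|---|
| 0 | (1.95/2)² = 0.95 | (24,875/25,000)² = 0.99 |
| 0.15 (6 of 40) | (1.8075/2)² = 0.82 | (24,518.75/25,000)² = 0.96 |
| 1 (nobody) | (1/2)² = 0.25 | (22,500/25,000)² = 0.81 |

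Simulation (400 replicates, mean volume 500 mL) agrees: at f = 0.10 it gives 0.856 to 0.969 against 0.860 to 0.971 from the formula.

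**2. One mean per volunteer, in mL.** If nobody tracks, r² = [s_b²/(s_b² + s_w²/60)]². This is (10,000/10,166.7)² = 0.967 for 100/100 and (22,500/22,541.7)² = 0.996 for 150/50. This unit of analysis carries almost no information on tracking.

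**3. Both instruments normalised within volunteer.** r² = [(1−f)ρ]². With f = 0 it is 0.95² = 0.90; with f = 0.15 it is (0.85 × 0.95)² = 0.8075² = 0.65. The fall is visible.

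**4. Limits of agreement.** Widening factor = √{[(1−f)(1−ρ) + f]/(1−ρ)}. At f = 0.15 this is √(0.1925/0.05) = 1.96 with ρ = 0.95, and √(0.235/0.10) = 1.53 with ρ = 0.90.

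**5. Can the overall figures tell the two situations apart?** Suppose all 40 volunteers had a within-volunteer correlation of 0.8075. Normalised r² would again be 0.8075² = 0.65, and the limits would widen by √[(1 − 0.8075)/0.05] = √(0.1925/0.05) = 1.96. Both match 34 volunteers at 0.95 and 6 at zero.

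**6. The significance criterion.** The smallest significant |r|, two-sided 5%, is t/√(t² + n − 2). It is 0.040 for 2400 breaths treated as independent and 0.312 for 40 volunteer means.

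**7. Can the data already planned show it?** Fisher z has SE 1/√(60 − 3) = 0.132. One volunteer's r = 0.9 then has 95% CI 0.84 to 0.94, and r = 0 has about −0.25 to 0.25. If correlation between successive breaths left only 20 effective breaths, the intervals would be 0.76 to 0.96 and −0.44 to 0.44, still separate. The share of volunteers who track can be given with an exact 95% CI: 40 of 40 gives 91.2% to 100%, and 36 of 40 gives 76.3% to 97.2%.

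**The case against.** A reader might infer that the plan averages over volunteers, that a failing minority must stay hidden, and that no planned output could contradict consistency. The documents do not support that much.

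- The unit of analysis is unstated. Singular wording suggests one overall analysis but does not fix it. The defect is silence, not a chosen averaging method.
- Masking depends on the scale. It is strong in mL; with both instruments normalised within volunteer, r-squared falls clearly. If relative Linshom values were pooled against ventilator mL, r² = ρ²s_w²/(s_b² + s_w²) would be only 0.9025 × 0.1 = 0.09 to 0.9025 × 0.5 = 0.45 with everyone tracking, so there would be no good overall figure to hide behind.
- A Bland-Altman plot shows individual points, and its limits widen about 1.5- to 2-fold in the example. It can therefore count against consistency.
- Consistency might instead mean stability over time or across volumes.
- The protocol documents no mechanism or rate of failure in individual wearers. Quiet breathing can also give a low within-person correlation because the volume range is narrow, without any device fault.

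These points stand, and they limit the claim. They do not supply the missing result. No reading of Statistical Methodology commits to per-volunteer output. Wider limits have no acceptance limit to be judged against, points need not be identified by volunteer, and step 5 shows that the overall figures cannot say which situation produced them.

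**Conclusion.** The concern holds in this form: the consistency half of the primary aim has no planned measure, and under one natural reading of the plan (breaths pooled in mL) r-squared can stay high although a minority does not track. In the example it is 0.82 to 0.96 with 15% of volunteers not tracking, and differences between volunteers alone give 0.25 to 0.81. The significance criterion offers little protection.

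The sizes rest on assumed SDs, correlation and breathing rate, and on non-trackers being centred on their own mean. The protocol gives none of these. The 15% is an illustration, not an expected failure rate. The gap itself does not depend on these assumptions. It would be wrong to say that failure is bound to be concealed, or that the Bland-Altman plot is blind to it.

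**What to change.** Before analysis, amend Statistical Methodology to:

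1. Define consistency as tracking within each volunteer, and state the unit of analysis.
2. State one scale, mL or relative, and reconcile Study Design with Statistical Methodology.
3. Report within-volunteer r, slope, bias and limits of agreement with 95% CIs for each of the 40, allowing for correlation between successive breaths.
4. Fit a random-slope mixed model and report the between-volunteer SD of the slope. Use repeated-measures Bland-Altman limits, with points identified by volunteer.
5. Set a tracking threshold in advance and report the proportion of volunteers who meet it, with its exact 95% CI. A rule that counts failure only when the CI for r includes zero is too lenient: with 60 breaths any r above about 0.25 passes. Read the proportion alongside each volunteer's tidal volume range, because only normal breathing is studied.
6. Base any conclusion about consistency on items 3 to 5.

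The cost is some SAP wording, a table or forest plot and one further model, all from data already to be collected. The downside is a possibly less favourable conclusion.

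### Breath depth is not varied by plan and the two devices have no common scale, so tracking is tested only over whatever volumes normal breathing happens to produce

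*Combined protocol and SAP*

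**What the plan says.** The Purpose is "To determine whether a non-invasive, temperature-based respiratory instrument could track tidal volume (V_t) in patients". The Specific Aim is whether the device "can accurately and consistently track tidal volume as measured by closed loop mechanical ventilator". The Background gives the motive: "Knowing the tidal volume before the carbon dioxide tension begins to increase provides an opportunity to intervene".

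The design is narrower. Under Inclusion Criteria, "Healthy volunteers 18 years of age or older will be recruited". Under Study Design, "The volunteers will be instructed to breathe normal through the CPAP mask on room air". Under Study Endpoints, "The subjects will breathe through the mask for about 5 minutes". No section plans shallow, deep or stepped breathing, or ventilator settings meant to change volume.

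Two sentences describe the comparison, in different terms. Study Design: "The temperature profiles from the sensors and the relative tidal volume will be correlated with the tidal volumes measured by the ventilator". Statistical Methodology: "We shall correlate the tidal volumes measured with the Linshom detector with the respective tidal volumes from the mechanical ventilator", followed by a least squares regression with r-squared and a Bland-Altman plot. The Abstract says the device normalises its signal to the person's own breathing. No section names the reference period or puts the ventilator on the same footing.

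**The concern.** To track a quantity is to follow it as it changes, and this plan schedules no change. Three consequences follow.

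- For a fixed device error, r-squared rises and falls with the spread of true volumes. A modest value could mean a poor device or a narrow range.
- Bland-Altman limits are much less sensitive to range, but they describe agreement only at the volumes that occurred, and the two readings must be in the same units.
- Setting a relative reading against an absolute one, pooled over volunteers, can lower r-squared because people differ in size of breath, whatever the device's accuracy.

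At stake is how far the result reaches. The motive concerns falling tidal volume in patients. The data will come from healthy people breathing as usual.

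**Working it through.** The only planned number is 40 volunteers, and it comes with no derivation, so there is no figure of the plan's own to reproduce. What follows is illustration.

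**Inputs.** From the documents: 40 volunteers and about 5 minutes each. Assumed, because the documents give none: within-person breath CV 10 to 30%; device error SD e of 10 to 20% of baseline, constant and additive with unit slope; 15 breaths per minute; added periods averaging m = 0.7 and 1.3 times baseline; equal numbers of breaths in the three periods; between-person CV B = 20% where pooling is considered.

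**1. Within-person r-squared.** Normal breathing: CV²/(CV² + e²). With added periods: v/(v + e²), where v = var(m) + CV² × mean(m²). Here var(m) = (0.09 + 0 + 0.09)/3 = 0.06 and mean(m²) = (0.49 + 1 + 1.69)/3 = 1.06.

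Worked case, CV 10% and e 15%: normal 0.01/(0.01 + 0.0225) = 0.31. Varied: v = 0.06 + 0.0106 = 0.0706, and 0.0706/0.0931 = 0.76.

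| CV (e = 15%) | Normal | With added periods |
|---|---|---|
| 10% | 0.31 | 0.76 |
| 15% | 0.50 | 0.79 |
| 20% | 0.64 | 0.82 |
| 30% | 0.80 | 0.87 |

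Over e = 10 to 20%, the ranges at CV 10 to 20% are 0.20-0.80 and 0.64-0.91. At CV 30% they are 0.69-0.90 and 0.80-0.94.

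Equal thirds flatter the change if the added periods are short. With 60% of breaths at usual depth and 20% in each added period (a further assumption), var(m) = 0.036 and mean(m²) = 1.036. At e = 15% this gives 0.0464/0.0689 = 0.67 at CV 10% and 0.0774/0.0999 = 0.77 at CV 20%.

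**2. Pooled, both devices in absolute units.** r² = V/(V + (1 + B²)e²), with V = B² + (1 + B²)s and s = CV² or v. At e = 15%, (1 + B²)e² = 1.04 × 0.0225 = 0.0234.

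- CV 10%: normal 0.0504/0.0738 = 0.68; varied 0.1134/0.1368 = 0.83.
- CV 20%: normal 0.0816/0.1050 = 0.78; varied 0.1465/0.1699 = 0.86.

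Differences between people supply some of the missing range, so the gain is smaller.

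**3. Relative device against absolute ventilator, pooled.** r² = CV⁴/(V × (CV² + e²)). At CV 10%, e 20%, B 20%: 0.0001/(0.0504 × 0.05) = 0.04. The same device gives 0.0504/(0.0504 + 0.0416) = 0.55 with both in absolute units, and 0.01/0.05 = 0.20 within person. Scale alone moves the answer.

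**4. What the Bland-Altman limits cover.** The limits are ±1.96e, or ±29.4% of baseline at e = 15%, in either design. The central 95% of volumes they describe differs:

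| CV | Normal | With added periods |
|---|---|---|
| 10% | 0.80-1.20 | 0.60-1.49 |
| 20% | 0.61-1.39 | 0.49-1.67 |
| 30% | 0.41-1.59 | 0.36-1.87 |

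**5. Small breaths recorded.** 40 × 5 × 15 = 3000 breaths. In normal breathing, 3000 × Φ(-0.3/CV) fall below 70% of baseline: 4, 68, 200 and 476 at CV 10, 15, 20 and 30%. With equal thirds the counts are 501, 524, 577 and 721. Below half of baseline they are 0, 1, 19 and 143, against 2, 29, 84 and 238, so the moderate range fills more than the extreme.

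**6. Normalisation.** If each device is divided by its own mean over the same period, both means are 1 and the mean difference there is exactly zero. A session that serves as its own reference can show limits but not bias.

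**The case against.** The strongest reply is that this is partly a matter of scope. Neither the Purpose nor the Specific Aim names a range of volumes or low volumes, and the Background sentence is motivation, not an endpoint. A first bench-style comparison in healthy volunteers may fairly stay with ordinary breathing. That stands. It is why narrowing the stated aim is an acceptable alternative to changing the session.

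The size can also be disputed. The larger gains are for a within-person analysis that Statistical Methodology does not specify; pooling in absolute units roughly halves the gain or better. If normal breathing has CV 30%, much of the range is already present. Bland-Altman is already planned and, on a common scale, could tell narrow spread from a poor device. All of this stands. Against it, the device output is described as relative, so absolute pooling may not be available, and no common scale is given.

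A reader might infer that the device would fail at small volumes, or that the trial cannot show tracking at all. The documents support neither. Spontaneous breathing varies, so some tracking will be visible. The model above assumes a linear device with constant error, under which small breaths reveal no new bias; failure there would need non-linearity, on which the documents give no data.

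**Conclusion.** The concern holds in limited form: the plan leaves the range of tidal volumes to chance and defines no common scale, so its results will speak to the volumes that happened to occur. At e = 15% and CV 10 to 20%, within-person r-squared is 0.31-0.64 without planned variation and 0.76-0.82 with it in equal thirds. The gain shrinks with shorter added periods, at CV 30%, or under absolute pooling. Every one of these figures rests on assumed CVs, error SDs and depths, and none measures performance at small volumes.

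The mismatch between patients in the Purpose and healthy volunteers in the Inclusion Criteria is a minor wording point, since the enrolled population is stated plainly. It should not be read as a claim that patients are studied. Overall this is a cheap improvement, not a flaw that invalidates the trial.

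**What to change.** **(a) Study Design.** Keep about 5 minutes of usual breathing, then add: *Volunteers will next breathe for two periods of [stated length], one at a self-selected smaller depth and one at a self-selected larger depth, in an order alternated or randomised across volunteers, followed by a brief return to usual depth. Period starts and ends will be marked in both data streams, and the ventilator volumes reached in each period will be reported.* Varying the order keeps depth from being mixed with time, and the return period checks sensor or mask drift. Amend the session length in Study Endpoints to match.

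**(b) Statistical Methodology, and the correlation sentence in Study Design.** *Each device will be expressed relative to its own mean over the same volunteer's initial usual-depth period. Within-person regression and r-squared will be reported, with Bland-Altman bias and limits by period and overall, allowing for repeated breaths per person.* Bias is zero by construction in the reference period and is read from the others.

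If (a) is declined, still use one within-person scale, with an opening part of the session (for example the first minute) as reference. Keep the repeated-breath analysis, and limit the Purpose and Specific Aim to normal breathing.

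**(c) Purpose.** Replace patients with healthy volunteers in either case.

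**Cost.** An IRB amendment, a few more minutes per volunteer and a short rewrite; equipment and staff are unchanged. Coached breaths are less natural, and self-selected depth widens the range without fixing it. A full 5-minute reference (75 breaths at the assumed rate) leaves scale uncertainty of e/√75 = 1.2 to 2.3% per volunteer. A one-minute reference (15 breaths) leaves e/√15 = 2.6 to 5.2%. Item (c) is a text edit only.

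### Does the lack of a described common clock or pairing rule undermine the comparison of Linshom and ventilator tidal volumes?

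*Combined protocol and SAP*

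**What the plan says.** Study Design sends the two series to different places. The thermistor excursions "will be recorded by the Linshom device and displayed continuously on a laptop monitor in a waveform". For the reference, "The tidal volume will also be measured by the ventilator and the data downloaded in a Compact Flash card". The same section adds that "The temperature profiles from the sensors and the relative tidal volume will be correlated with the tidal volumes measured by the ventilator", and that "The volunteers will be instructed to breathe normal through the CPAP mask on room air".

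Study Endpoints gives about 5 minutes of continuous data per volunteer and says "the data will be analyzed post-hoc". Statistical Methodology pairs the Linshom values "with the respective tidal volumes from the mechanical ventilator", using least squares with r-squared, a Bland-Altman plot and P<0.05. The Abstract describes the Linshom signal as "measuring the excursions of the temperature swings between inspiration and expiration and normalizing them to the patient's breathing". Forty volunteers are planned.

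The protocol does not mention clock setting, a common trigger, an event marker, the unit of pairing, an averaging window, or missed and extra breaths. Equally, it does not say that the recorders are unsynchronised, that pairing is breath by breath, or that alignment will be chosen by goodness of fit.

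**The concern.** Any correlation between two recorders depends on matching the right values. Two devices with no stated common time base, and steady breathing with no imposed change in volume, leave few landmarks. If alignment is settled only after the sessions, there are two possible errors:

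- An undetected offset could make a good device look poor, both in r-squared and in the limits of agreement.
- Sliding one trace until it best fits the other would use the outcome to define the pairs, and could give a worthless device a significant result.

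A marker that was not recorded cannot be added afterwards, and the study lasts only one week. Because the Linshom signal is normalised to each person's own breathing, the within-volunteer case, where pairing matters most, is the plausible one.

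**Working it through.** The protocol gives no target correlation, autocorrelation or between-volunteer variance, so there is no stated figure to reproduce. From the protocol: 40 volunteers, about 5 minutes each, P<0.05. Assumed: 15 breaths per minute, hence 15 × 5 = 75 breaths per volunteer and 40 × 75 = 3,000 in all; tidal volume as a first-order autoregressive series with lag-1 autocorrelation φ; device reading = ρ × volume + noise.

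**1. One-breath offset, within volunteer, ρ = 0.90.** The expected r is about ρφ. Simulated values run slightly lower because the series are short.

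| φ | ρφ | simulated r |
|---|---|---|
| 0.1 | 0.09 | 0.07 |
| 0.3 | 0.27 | 0.25 |
| 0.5 | 0.45 | 0.42 |
| 0.7 | 0.63 | 0.59 |
| 0.9 | 0.81 | 0.73 |

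On a common scale the SD of the differences is √(2(1 − r)). It is √0.20 = 0.45 when aligned and √1.50 = 1.22 at r = 0.25, so the limits of agreement widen about 2.7 times.

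**2. The loss depends on the unit of analysis.** If absolute volumes are pooled and a share *b* of the variance lies between volunteers, the offset r is about 0.90 × (b + (1 − b)φ). With φ = 0.2, b = 0.3, 0.5 and 0.7 give 0.40, 0.54 and 0.68 (simulated 0.39, 0.53, 0.67). With 30-second averages at φ = 0.3, an offset lowers r only from 0.94 to 0.85. One breath is 60/15 = 4 s of a 30-s window.

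**3. Can a constant offset be found afterwards?** Searching ±5 breaths over a 75-breath record, with φ from 0 to 0.5:

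| true r | correct lag found | upward bias in r |
|---|---|---|
| 0.7 to 0.9 | 100% | under 0.001 |
| 0.5 | 96 to 99% | about 0.002 or less |
| 0.3 | 69 to 80% | about 0.02 |

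Steps 1 and 3 work against each other. At low φ, adjacent lags give about 0.90 and 0.25, so the error is obvious. At high φ the lags are harder to tell apart, but the error costs much less.

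**4. Unrelated device, best lag chosen for each volunteer (φ = 0.2).**

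| window (breaths) | mean r | r² of that mean |
|---|---|---|
| ±1 | 0.09 | 0.008 |
| ±3 | 0.16 | 0.026 |
| ±5 | 0.20 | 0.038 |
| ±10 | 0.26 | 0.068 |

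At φ = 0.5 and ±10 breaths the mean r is 0.28, r² 0.078. Pooled nominal P<0.05 occurs in essentially every simulated study (97% in the mildest case, ±1 at φ = 0.5). Much of this comes from treating 3,000 breaths as independent: the critical |r| is then about 1.96/√3000 = 0.036. Within a single volunteer the rate at ±5 breaths is 26%; eleven independent lags would give 1 − (1 − 0.025)^11 = 24%.

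**The case for a change.** The strongest counter-argument is that step 3 assumes one constant offset per record. If Linshom misses a single breath at a random point among 75 and the series are paired by order, a true r of 0.90 falls to 0.48, 0.58 or 0.66 at φ = 0.1, 0.3 or 0.5. The best single shift within ±5 breaths restores only 0.69, 0.74 or 0.78. Times on a common base would solve this, and matching clocks and recording a marker looks cheap. P<0.05 is also the only acceptance criterion the protocol states, and it is the one that lag selection defeats.

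Part of this stands. No single shift repairs a dropped breath, and a marker would be convenient. But pairing by breath order is another step the protocol does not contain. Both series are described as continuous, so if the files keep breath times a missed breath should show as a long interval and can be handled by timing without reference to amplitude. Such matching works when timing jitter is small relative to the variation in breath interval, and fails when it is large; the protocol does not tell us which applies. An uncorrected dropped breath lowers r, so it understates a good device and does not flatter a bad one. Whether the recorders accept a marker is not stated either, so its cost is unknown. The weakness of P<0.05 with pooled breaths is a separate matter that synchronisation would not cure.

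**Conclusion.** No change to the plan is needed. The protocol leaves synchronisation and pairing unwritten, but no rule it does state produces a wrong answer. Analysing the data after the session does not mean alignment is chosen to suit the result.

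The large loss (r from 0.90 to about 0.07 to 0.25) needs four things together: breath-level pairing, within-volunteer analysis, autocorrelation of about 0.1 to 0.3, and an offset that nobody notices. Under those same conditions the offset is easiest to notice. At autocorrelation of 0.7 to 0.9, r remains 0.59 to 0.73. The opposite error needs a fit-driven step that is not planned, and its product, r of about 0.1 to 0.3, would be exposed by the planned r-squared and Bland-Altman plot.

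These sizes rest on assumed breath rates, autocorrelations and true correlations, and on a constant offset in the recovery calculation. What remains is missing procedural detail that analysts can fill sensibly by pairing on time, accounting for unmatched breaths and not tuning the alignment to the correlation.
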